8.2. Premature Subject Withdrawal

Early withdrawal (discontinuation of treatment) occurs when an enrolled subject ceases participation in the trial, regardless of the circumstances, prior to the expected completion of the trial. Additionally, the investigator may discontinue the treatment of a subject at any time if he/she considers it to be in the subject's best interest. If significant safety issues arise, dosing may be discontinued but unless informed consent is withdrawn any subject who discontinues treatment with either TransCon hGH or Genotropin should be encouraged to remain in the trial and attend all clinic visits. The final decision for treatment discontinuation will be made by the Medical Expert and investigator. See [Section 7.3](#) for a list of stopping rules governing early termination of subjects from trial.

In the case of premature discontinuation of a subject's participation in the trial (eg, withdrawal of informed consent), the investigator should schedule a trial discontinuation visit to collect data, particularly AE follow-up data (if applicable) and to collect samples for laboratory evaluations. This visit should contain assessments from the End of Trial Visit (Visit 6, Day 365), and should

be documented in the eCRF together with the reason for trial discontinuation. In case of treatment discontinuation for other causes than withdrawal of the informed consent, subjects should be asked to remain in the trial and attend all subsequent trial visits.

Every effort should be made to observe subjects who have been randomized and received at least 1 dose of study drug until the scheduled end of their observation, even if they discontinued the trial treatment. The investigator should make every attempt to contact the subject/parent/legal guardian via phone to arrange the appropriate follow-up assessment for such subjects and document the course of the subject's condition.

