2.2.3 Pharmacokinetic/Pharmacodynamic Variable(s)

The pharmacokinetic (PK) variables (endpoints) are:

Subset of at least 8 TransCon hGH treated subjects after 13 weeks of treatment:

- PK profile of TransCon hGH over 1 week
- PK profile of hGH over 1 week
- PK profile of PEG over 1 week
- C_{max} for hGH of TransCon hGH

The pharmacodynamic (PD) variables (endpoints) are:

- PD profile of IGF-1 and IGFBP-3 over 1 week
- PD profile of IGF-1 SDS and IGFBP-3 SDS over 1 week

3. Overall Study Design and Plan

This is a phase 3, randomized, open-label, active-controlled trial of TransCon hGH as compared to standard daily growth hormone, over 52 weeks (Figure 1). The trial will be conducted at approximately 100 sites in approximately 20 countries in North America, Europe, Middle East and North Africa, and Oceania. All centers will be specialized treatment centers in the management of pediatric GHD.

The trial consists of:

[figure not shown]
- Screening period - up to 6 weeks (plus approximately 2 weeks between randomization and V1)
- Treatment period - 52 weeks of dosing

The total duration of participation for each subject in the trial will therefore be up to about 60 weeks.

PK/PD profiling and electrocardiogram (ECG) screening bracketing presumed C_{max} of TransCon hGH, hGH, IGF-1, and PEG will be established in a subset of at least 8 TransCon hGH treated subjects (PK/PD subset).

All subjects who successfully complete the 52-week randomized trial will be invited to participate in an extension trial after the treatment period of this 52-week trial has ended. This extension period is to assess long-term safety and efficacy. Subjects on Genotropin treatment (Cohort 2) will be switched over to TransCon hGH treatment for this extension trial.

Figure 1

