4.2 Final Analysis

All final, planned analyses identified in the protocol and in this SAP will be performed after the last subject has completed the last study visit and end of study assessments, and all relevant study data have been processed and integrated into the analysis data base. Any results from unplanned analyses (post-hoc) will be clearly identified in the text of the CSR.

5. Analysis Populations

The following analysis populations are planned:

Safety Analysis Population: The safety analysis population will include all randomized subjects who have received at least 1 dose of active treatment.

Intention-To-Treat Population (ITT): The Intent-to-Treat population will include all randomized subjects who have received at least one dose of active treatment

Pharmacokinetic/Pharmacodynamic Population (PK/PD): The PK/PD Population includes all subjects in the Safety Population who have PK/PD assessments. The PK/PD profile subset comprise a subset of subjects pre-identified as the PK/PD subset from the TransCon hGH cohort who attended Visit 3 as planned, and from whom blood samples were taken at time points predose, 8, 12, 16, 24, 36, 48, 72, 96, 120, and 168 hours postdose. All subjects in the safety analysis population with additional PK/PD samples will be included in additional PK/PD analyses.

Per Protocol Population (PP): The basis of PP population is the ITT population who have relevant data evaluable for the primary efficacy endpoint of annualized HV at 52 weeks. Specifically, subjects were excluded from the PP population if they:

- Had a diagnosis known to impact growth (exclusion criteria 4, 5, 6, 10, 12, 13)
- Took the wrong treatment (eg. randomized to TransCon hGH cohort but took Genotropin in error)
- Missed or overdosed on at least 5 doses of TransCon hGH, or 35 doses of Genotropin
- Used prohibited concomitant medications at trial entry (exclusion criteria 15, 16)
- Failed to have a height measurement at the Week 52 visit

Given that the primary objective of the study is based on testing for non-inferiority, the primary efficacy analyses will be performed on both ITT and PP populations. The primary analysis population is the ITT population. The ITT population will be analyzed on the basis of the intention to treat a subject, i.e. the planned treatment regimen. The PP subset will be analyzed on the basis on the actual treatment given.

The safety analyses will be based on the Safety Analysis Population.

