6.1.3 Visit Windows

Table 2: Bioanalytical Samples visit windows from Visits 1 to 6

Visit	Time Relative to Dosing, by Visits (Hours)					
	1	2	3	4	5	6
TransCon hGH	predose, morning	predose, morning	48-72h, morning	48-72h, morning	48-72h, morning	164-172h, morning
Week	1	5	13 (+2)	26 (±1)	39 (±1)	52 (+1)
Day	1	29	87-88	178-179	269-270	365
Genotropin	predose, 2h, morning	morning	morning	morning	morning	morning
Week	1	5	13 (+2)	26 (±1)	39 (±1)	52 (+1)
Day	1	29-35	85-91	176-182	267-273	365

Abbreviation: hGH=human Growth Hormone

TransCon hGH Cohort (Cohort 1)

- Visits 1 and 2 will be performed on the day of the 1st and 5th dosing (Days 1 and 29), respectively.
- Visits 3, 4 and 5 will be performed 48-72 hours after the 13th, 26th and 39th dose, respectively.
- Visit 6 will be performed 7 days after the last dose (Day 365).

All attempts should be made to adhere to the planned visit schedule as specified per [Table 2](#). However, in case the subject is not able to attend Visits 3, 4, 5 and 6 during Week 13, 26, 39 or 52, respectively, these visits can be performed with a + 2 week window for Visit 3, meaning either Week 14 or 15, if Week 13 is not achievable; and a ± 1 week window for Visits 4, and 5, meaning either Week 25 or 27, if Week 26 is not achievable or Week 38 or 40, if Week 39 is not achievable; and a + 1 week visit window for Visit 6, meaning Week 53, if Week 52 is not achievable.

Genotropin Cohort (Cohort 2)

- At Visit 1, subjects will be dosed in the morning at the clinic.
- All subjects in the Genotropin cohort will attend Visit 1 fasting with administration of the dose at the investigational site and predose sampling and will have an additional postdose sampling for hGH at 2 hours.
- Visits 2, 3, 4 and 5 will be performed on any day during Weeks 5, 13, 26 and 39, respectively. Preferably, all clinic visits will be in the morning for consistency of auxology measurements. Visit 4 needs to be conducted in the morning hours, since the subject is requested to be fasting. Visit 6 will be performed 1 day after the last dosing (Day 365) in the morning hours, since the subject is requested to be fasting.

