6.2 Derived and Computed Variables

The following derived and computed variables have been initially identified as important for the analysis of the safety, efficacy or PK/PD as appropriate. It is expected that additional variables will be required. The SAP will not be amended for additional variables that are not related to the primary target or key secondary target variables. Any additional derived or computed variables will be identified and documented in the SAS programs that create the analysis files.

Parameter	Description of Parameter
Date of Birth	Day of 15 is used to impute the day for all birth date
Age (Years)	$(\text{Date of Measurement} - \text{Date of Birth}) / 365.25$
Age (Months)	$((\text{Date of Measurement} - \text{Date of Birth}) / 365.25) * 12$
C _{max}	The maximum serum concentration observed.
Annualized Height Velocity at visit x (HV) cm/year	$[(\text{HT}(\text{Visit } x) - \text{HT}(\text{Visit } 1))] * 365 / [(\text{Date}(\text{Visit } x) - \text{Date}(\text{Visit } 1))]$
Change from baseline over 52 weeks	The value of each variable at each post-baseline timepoint minus the baseline score. The change from baseline will be calculated for: 
 • change in height (HT) SDS • change in serum IGF-1 • change in serum IGFBP-3 • change in IGF-1 SDS • change in IGFBP-3 SDS
Normalized serum IGF-1 SDS	Proportion of subjects with IGF-1 Standard Deviation Score (SDS) of 0 to +2.0. Also derive for -2.0 to +2.0, -1.0 to +2.0.

Parameter	Description of Parameter
Total duration of treatment (day)	
TransCon hGH Last dose date – first dose date + 7
 
Genotropin Last dose date – first dose date + 1

Total number of planned doses	
TransCon hGH Round (Last dose date – first dose date + 7)/7 to the nearest integer
 
Genotropin Last dose date – first dose date + 1

Total Actual Dosage (mg)	
TransCon hGH Sum Concentration (mg/mL) x volume (mL) over all injections
 
Genotropin Sum dose (mg) over all injections

Parents' Height SDS	
$((\text{Parents Height}/M)^L - 1)/(L \times S)$
 
Where M=median , S= generalized coefficient of variation, and L= power in the Box-Cox transformation, the M, S, L values are obtained from the CDC website; Percentile Data Files with LMS Values

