9.11 Exposure and Compliance

For each subject, the individual extent of exposure will be calculated in terms of:

- Total duration of treatment
- Total number of planned doses
- Total number of actual doses
- Actual Total dosage (mg)

These variables will be listed by subject, sorted by treatment group and subject number. Summary statistics per treatment group will be tabulated overall.

For the TransCon hGH group, subjects whose weekly actual dosage (mg/kg/wk) differ from the planned weekly dosage of 0.24 mg/kg/wk will be identified and followed for potential explanation.

Study drug compliance will be calculated as:

Total number of doses taken /total number of planned doses

Compliance will be summarized using the following categorization; <80%, ≥80%, ≥90%, ≥95% and ≥100%

Exposure and compliance will be listed by subject and presented for the safety population set by means of summary statistics by treatment group.

10. Changes from Planned Analysis

No changes from planned analysis.

11. Other Planned Analyses

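### SAP 6.2 counts planned doses only to the last dose taken, so early stopping never lowers reported compliance, and the per-protocol missed-dose rule may share the blind spot

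*SAP*

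**What the plan says.** SAP 6.2 (Derived and Computed Variables) gives one planned-dose count per arm. For TransCon hGH it is "Round (Last dose date – first dose date + 7)/7 to the nearest integer"; for Genotropin it is "Last dose date – first dose date + 1". Both end at the date of the last dose actually taken. SAP 9.11 (Exposure and Compliance) defines compliance as "Total number of doses taken /total number of planned doses" and tabulates it by arm in bands from below 80% up to 100% or more. Protocol 13.4.2 leaves the definition of compliance to the SAP, so no other definition overrides this one.

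The intended course is stated in SAP Section 3: "Treatment period - 52 weeks of dosing".

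SAP Section 5 (Analysis Populations) removes a child from the per-protocol (PP) set for, among other reasons, this one: "Missed or overdosed on at least 5 doses of TransCon hGH, or 35 doses of Genotropin". It does not say against which count a dose is missed. No PP criterion names stopping study drug. A separate criterion removes any child without a height at the Week 52 visit.

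Protocol 8.2 says that after a treatment stop for reasons other than withdrawn consent, "subjects should be asked to remain in the trial and attend all subsequent trial visits". SAP Table 3 (Section 6.1.3) maps an early termination visit on Day 318 or later to Week 52.

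**The concern.** A compliance ratio should fall when part of the planned course is not given. This one responds to gaps before the last dose and ignores every omission after it. A child who takes each dose and then stops halfway is recorded as fully compliant. Protocol 5.4 presents better adherence as a main benefit of weekly dosing, so readers will compare this ratio between arms.

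The same count may reach the PP set. SAP Section 5 runs the primary efficacy analysis in both ITT and PP because the objective is non-inferiority, so the PP set is meant to show growth on treatment. The 6.2 variable is the only planned-dose count the SAP defines, and a programmer would naturally use it to count missed doses. On that reading, a child who is off drug for weeks or months but has a Week 52 height meets the dosing criterion.

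**Working it through.** **Inputs.** Planned-dose formulas: SAP 6.2. Compliance: SAP 9.11. Course length: 52 weeks (SAP Section 3), that is 52 weekly or 52 × 7 = 364 daily doses. Timing of the last dose in a completer: SAP 6.1.3, Day 358 for TransCon hGH (7 days before Day 365) and Day 364 for Genotropin ("Visit 6 will be performed 1 day after the last dosing (Day 365) in the morning hours"). PP limits: 5 and 35 (SAP Section 5).

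**Completers first.** TransCon hGH: round((358 − 1 + 7)/7) = round(364/7) = 52. Genotropin: 364 − 1 + 1 = 364. Both match the 52-week course, so the formulas are right for a child who finishes.

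**Children who take every dose and then stop.** Weekly dose *k* falls on Day 1 + 7(*k* − 1), so planned = round((7(*k* − 1) + 7)/7) = *k*, which equals doses taken. For a daily stop on Day *d*, planned = *d*, again equal to doses taken.

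| Last dose | Planned (6.2) | Compliance (9.11) | Missed (planned − taken) | Share of schedule | Not given |
|---|---|---|---|---|---|
| Weekly 13 (Day 85) | 13 | 100% | 0 | 13/52 = 25% | 39 |
| Weekly 26 (Day 176) | 26 | 100% | 0 | 26/52 = 50% | 26 |
| Weekly 39 (Day 267) | 39 | 100% | 0 | 39/52 = 75% | 13 |
| Weekly 44 (Day 302) | 44 | 100% | 0 | 44/52 = 85% | 8 |
| Daily, Day 91 | 91 | 100% | 0 | 91/364 = 25% | 273 |
| Daily, Day 182 | 182 | 100% | 0 | 182/364 = 50% | 182 |
| Daily, Day 273 | 273 | 100% | 0 | 273/364 = 75% | 91 |

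**Gaps before the last dose do count.** A completer who misses 6 weekly doses mid-trial has 46/52 = 88.5% and 6 missed. A child with 3 gaps who stops at week 26 has 23/26 = 88.5% and 3 missed, against 23/52 = 44% and 29 doses short of the schedule. The ratio is the same for very different exposure.

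**PP set.** The limits are the same share of the course in both arms: 5/52 = 35/364 = 9.6%. Two routes keep a child who stopped in the PP set when missed doses are counted through 6.2:

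- *Observed Week 52 height off drug.* Stop at week 26 and attend Visit 6: 0 missed through 6.2, below 5, so kept. Against the schedule, 26 missed, so excluded.
- *Mapped visit.* Last weekly dose 46 on Day 316, termination visit on Day 323, mapped to Week 52 by Table 3: 46/46 = 100%, 0 missed. Against the schedule, 52 − 46 = 6 missed. The child is kept if a mapped visit counts as the Week 52 visit, which the SAP does not say.

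Measured against the schedule, the limit is reached when the last dose is weekly dose 47 (Day 323) or earlier, since 52 − 47 = 5, or Day 329 or earlier on Genotropin, since 364 − 329 = 35.

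**Size on documented facts.** The version 5.0 entry in the SAP history reports two early discontinuations and does not give their dates or arms. The overstatement for one child is below 100 percentage points, provided doses taken do not exceed the planned count. If both were in one arm, the arm mean is overstated by less than 2/100 = 2 points (TransCon hGH, about 100 children) or 2/50 = 4 points (Genotropin, about 50). If both stopped halfway with no gaps, the figures are 1 and 2 points.

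**The case against.** Four points can be made for the plan.

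First, the PP criterion does not cite 6.2. Missed doses can equally be read against the stated 52 weeks, using the dose dates in the Subject Diary (Protocol 9.8); the child who stops at week 26 is then excluded. SAP 6.2 also allows further derived variables to be documented in the programs. This stands: the PP problem is an undefined term, not a stated rule.

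Second, a reader might infer that any child who stops early is kept in the PP set. The documents do not support that. Without a Week 52 height the child is excluded whatever the dose count. The SAP history reports no retrieved dropout and foresees imputation for both discontinued children, so both appear to leave the PP set. A family that stops injecting late without a recorded discontinuation cannot be ruled out, but nothing shows that it happened.

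Third, a reader might infer that early stopping is invisible in the report. It is not. SAP 9.11 summarises treatment duration and actual doses by arm, Tables 14.3.4.10.2.1 and 14.3.4.10.2.2 give exposure by week and by day, and SAP 7.1 reports disposition with reasons. Only the compliance ratio misses it.

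Fourth, compliance while on treatment is a usable measure, and it keeps non-adherence apart from stopping for medical reasons. This stands too, but the SAP calls its denominator planned doses and does not label the ratio as on-treatment.

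**Conclusion.** The compliance part holds as written in both arms: the denominator ends at the last dose, so stopping by itself never lowers the ratio. For a child with no earlier gaps the figure is 100% at any stopping point, against 50% of the course at week 26.

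The PP part is conditional. It requires a Week 52 height, observed or mapped, and a reading of missed doses through 6.2 that the SAP neither states nor excludes. No affected PP child is documented. The ITT primary analysis uses no planned-dose count and is not affected.

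This should be corrected because a defined variable gives a misleading figure and a PP criterion is open to two readings with opposite results. It does not threaten the primary conclusion. The size for documented discontinuations rests on the approximate arm sizes of 100 and 50; the number of unrecorded late stops is unknown.

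**What to change.** In SAP 6.2, count planned doses against the 52-week schedule: 52 weekly or 364 daily doses. Extend the count only when the scheduled Visit 6 falls in its +1 week window. Never shorten it for an early termination or mapped visit; otherwise the child with last dose 46 and a visit on Day 323 would again show 46/46 and no missed doses.

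Use this count as the denominator in 9.11, and cite it in SAP Section 5 as the definition of a missed dose, so that doses not given after stopping study drug count towards the limits of 5 and 35. State in the same place whether a visit mapped by Table 3 counts as the Week 52 visit. Keep the present ratio as a second line labelled on-treatment compliance.

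The cost is one derived variable and a few sentences. Stated compliance becomes slightly less favourable, doses not given after a medically required stop count as not taken in the schedule-based line (the on-treatment line and the disposition table keep that distinction visible), and any late stopper may leave the PP set.

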Region	
 • Australia and New Zealand will be mapped to 'Oceania' • Belarus, Bulgaria, France, Georgia, Germany, Greece, Italy, Poland, Romania, Russia and Ukraine will be mapped to 'Europe' • Canada and United States of America will be mapped to 'North America' • Egypt and Jordon will be mapped to 'Middle East and North Africa' • Turkey and Armenia will be mapped to 'Asia'
Height Velocity at Baseline	
Calculated based on the height measurement pre-dose, with the measurement closest to the time of one year before baseline if we have multiple height measurements before baseline. If the there are two measurements with equal distance to one year prior to baseline, we use the one closer to baseline of the two to calculate baseline height velocity

Parameter	Description of Parameter
Height SDS	Height expressed in Standard Deviation Score (SDS) is derived using CDC 2000 (United States of America)/Kuczmarski method as $((\text{Height}/M)^L - 1) / (L \times S)$. Where M=median , S= generalized coefficient of variation, and L= power in the Box-Cox transformation, the M, S, L values are obtained from the CDC website; Percentile Data Files with LMS Values. M, L, and S need to be interpolated based on the next lower age category, and the next upper age category.
Height Velocity SDS	The Height Velocity expressed in SDS is derived as follows. $\text{HV SDS} = (\text{Observed HV} - \text{Reference HV}) / \text{Reference HV SD}$. Mean age at the two visits where HV is calculated will be used to determine reference HV and HV SD. Mean HV and SD HV are defined by age categories between male and female as in the Tanner's publication [7a, 7b]. Reference HV and HV SD are interpolated based on the lower age category and the next upper age category and mean age

The following variables are automatically calculated in the eCRF. However, the reference methods for calculation are reported in the following table for completeness of information.

Parameter	Description of Parameter
Birth Weight SDS	The Birth Weight Standard Deviation Score is calculated in the eCRF using the method described in [8]

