8.2 Secondary Efficacy Variable Analysis

The absolute values and mean change from baseline at each timepoint of other secondary efficacy endpoints will be presented by treatment group with descriptive statistics. Height velocity SDS will also be summarized. Mixed model for repeated measurement (MMRM) models will be used for the following continuous secondary efficacy endpoints. Missing data will not be imputed before conducting the MMRM model. The MMRM model for height velocity will include baseline age, peak GH levels (log transformed) at stimulation test, baseline height SDS – average SDS of parental height, as covariates, gender as a fixed factor, and subject as a random effect. The MMRM model for all the following continuous variables will include treatment, timepoint, and treatment by timepoint interaction.

- height velocity
- change in height SDS
- serum IGF-1 levels
- serum IGFBP-3 levels
- IGF-1 SDS
- IGFBP-3 SDS

The MMRM model for change in height SDS, IGF-1, IGFBP-3, IGF-1 SDS and IGFBP-3 SDS will include baseline age, peak GH (log transformed), baseline (of the corresponding variable) as covariates, and gender as a factor.

For the patients who are in PK/PD population, the average values from hour 48 and hour 72 at Visit 3 (Week 13) will be considered as the Visit 3 value for IGF-1, IGF-1 SDS, IGFBP-3 and IGFBP-3 SDS, and used in the analyses for Visit 3.

Two sided 95% confidence intervals will be calculated for the difference in least square means between the 2 treatment groups. Change from baseline will be summarized when appropriate as supportive analyses.

The rate of subjects achieving normalization of serum IGF-1 SDS will be calculated by treatment group and visit defined as SDS scores of 0 to 2.0. Additionally, cut points of -2.0 to +2.0 and -1.0 to +2.0 will be assessed. The following IGF-1 SDS variables will be derived:

- Average IGF-1 SDS at visits 3, 4, and 5
- Proportion of subjects achieving normalization of IGF-1 SDS of 0 to 2.0 based on the average IGF-1 SDS at visits 3, 4, and 5

The rates of subjects achieving IGF-1 SDS 0-2.0 will be analyzed by logistic regression adjusting for baseline age and baseline IGF-1 SDS. In case of model convergence issues caused by sparse cells, Fisher's exact test will be carried out instead.

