13.2 EFFICACY DATA

Table 14.2.1.1	ITT/PP	Annualised height velocity by Visit: Observed Case, summary statistics
Table 14.2.1.2	ITT/PP	Annualised height velocity by Visit and Subgroup: Observed Case
Table 14.2.1.3	ITT/PP	Annualised height velocity by Visit: MMRM analysis, Observed Case
Table 14.2.1.6	ITT/PP	Annualised height velocity by Visit: Impute Missing Height Velocity after Dropout, summary statistics
Table 14.2.1.7	ITT	Annualised height velocity at by Visit: Sensitivity analysis MMRM analysis, Impute Missing Height Velocity after Dropout
Table 14.2.1.8	ITT/PP	Annualised height velocity by Visit: ANCOVA Analysis, Observed Case
Table 14.2.2.1	ITT	Height SDS by Visit: summary statistics
Table 14.2.2.2	ITT	Height SDS by Visit and Subgroup: summary statistics
Table 14.2.2.3	ITT	Change from baseline in Height SDS by visit: MMRM analysis
Table 14.2.2.4	ITT	Height Velocity SDS by Visit: summary statistics
Table 14.2.2.5	ITT	Height Velocity SDS by Visit and Subgroup: summary statistics
Table 14.2.3.1	ITT	Serum IGF-1 by Visit: summary statistics
Table 14.2.3.2	ITT	Serum IGF-1 by Visit and Subgroup: summary statistics
Table 14.2.3.3	ITT	Serum IGF-1 SDS by Visit: summary statistics
Table 14.2.3.4	ITT	Serum IGF-1 SDS by Visit and Subgroup: summary statistics
Table 14.2.3.5	ITT	Serum IGF-1 by visit: MMRM analysis
Table 14.2.3.6	ITT	Serum IGF-1 SDS by visit: MMRM analysis
Table 14.2.3.7	ITT	Normalisation of IGF-1 SDS by visit
Table 14.2.3.9	ITT	Average IGF-1 SDS at Weeks 13, 26, and 39

Table 14.2.3.10	ITT	Proportion of Subjects Achieving Normalization of IGF-1 SDS within 0 to 2.0 Based on Average IGF-1 SDS at Weeks 13, 26, and 39
Table 14.2.3.11	ITT	Average IGF-1 SDS at Weeks 13, 26, and 39 (Based on the Non-Linear Mixed Model TransCon hGH, Average for Genotropin): ANCOVA Analysis
Table 14.2.3.12	ITT	Average IGF-1 SDS at Weeks 13, 26, and 39 within 0-2.0 (Based on the Non-Linear Mixed Model TransCon hGH, Average for Genotropin): Logistic Regression Analysis
Table 14.2.4.1	ITT	Serum IGFBP-3 by Visit: summary statistics
Table 14.2.4.2	ITT	Serum IGFBP-3 by Visit and Subgroup: summary statistic
Table 14.2.4.3	ITT	Serum IGFBP-3 SDS by Visit: summary statistics
Table 14.2.4.4	ITT	Serum IGFBP-3 SDS by Visit and Subgroup: summary statistics
Table 14.2.4.5	ITT	Serum IGFBP-3 by visit: MMRM analysis
Table 14.2.4.6	ITT	Serum IGFBP-3 SDS by visit: MMRM analysis

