13.4 FIGURES

Figure 1	ITT	Annualized HV (LS Mean \pm SE) at Visit 6 (Week 52) for weekly TransCon hGH and daily hGH treatment groups
Figure 2	ITT	Distribution of Annualized HV at Week 52 for weekly TransCon hGH and daily hGH treatment groups
Figure 3	ITT	Annualized HV (Mean \pm SE) over 52 weeks for the TransCon hGH and the daily hGH treatment groups
Figure 4	ITT	Distribution of Annualized HV over 52 weeks for weekly TransCon hGH and daily hGH treatment groups
Figure 5	ITT	Delta Height SDS (LS Mean \pm SE) at Week 52 for weekly TransCon hGH and daily hGH treatment groups
Figure 6	ITT	Distribution of delta height SDS at Week 52 for weekly TransCon hGH and daily hGH treatment groups
Figure 7	ITT	Delta Height SDS (Mean \pm SE) over 52 weeks for the TransCon hGH and the daily hGH treatment groups
Figure 8	ITT	Distribution of delta Height SDS over 52 weeks for weekly TransCon hGH and daily hGH treatment groups
Figure 9	ITT	Height SDS (Mean \pm SE) over 52 weeks for weekly TransCon hGH and daily hGH treatment groups
Figure 10	ITT	Distribution of Height SDS over 52 weeks for weekly TransCon hGH and daily hGH treatment groups
Figure 11	ITT	Distribution of Height Velocity SDS over 52 weeks for weekly TransCon hGH and daily hGH treatment groups
Figure 12	ITT	Serum IGF-1 SDS (LS Mean \pm SE) over 52 weeks for weekly TransCon hGH and daily hGH treatment groups
Figure 13	ITT	Distribution of IGF-1 SDS over 52 weeks for weekly TransCon hGH and daily hGH treatment groups
Figure 14	ITT	Proportion of patients with normalized serum IGF-1 (0 – (+2.0) SDS) based on the average IGF-1 SDS at steady states for the TransCon hGH and the daily hGH treatment groups
Figure 15	ITT	Proportion of patients with normalized serum IGF-1 (0 – (+2.0) SDS) over 52 weeks for the TransCon hGH and the daily hGH treatment groups

- Figure 16 ITT Serum IGFBP-3 SDS (Mean \pm SE) over 52 weeks for weekly TransCon hGH and daily hGH treatment groups
- Figure 17 ITT Distribution of IGFBP-3 SDS over 52 weeks for weekly TransCon hGH and daily hGH treatment groups
- Figure 18 ITT Proportion of patients with normalized serum IGF-1 (-2.0 – (+2.0) SDS) over 52 weeks for the TransCon hGH and the daily hGH treatment groups
- Figure 19 ITT Proportion of patients with IGF-1 between -1.0 – (+2.0) SDS over 52 weeks for the TransCon hGH and the daily hGH
- Figure 20 ITT Distribution of Serum Concentrations of TransCon PEG40 hGH (ng hGH/mL) over 52 weeks for weekly TransCon hGH treatment group

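### Height velocity SDS uses a reference SD chosen by sex and age only, so Week 5 (28-day) and Week 52 (364-day) values cannot both be valid SD scores

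*SAP*

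**What the plan says.** SAP 6.2 defines HV SDS as observed HV minus reference HV, divided by the reference HV SD. Three sentences fix the reference values:

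- "Mean HV and SD HV are defined by age categories between male and female" (the SAP cites published British growth standards here);
- "Mean age at the two visits where HV is calculated will be used to determine reference HV and HV SD";
- "Reference HV and HV SD are interpolated based on the lower age category and the next upper age category and mean age".

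The lookup therefore depends on sex and age. The number of days between the two height measurements does not enter it.

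The observed value is defined in the same section under "Annualized Height Velocity at visit x (HV) cm/year": height at Visit x minus height at Visit 1, times 365, divided by the days between them. The definition is the same for every visit.

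SAP 8.2 then says "Height velocity SDS will also be summarized", with no restriction on visit. SAP 13.2 lists Table 14.2.2.4, "Height Velocity SDS by Visit: summary statistics", and Table 14.2.2.5, which repeats it by subgroup. SAP 13.4 lists Figure 11, "Distribution of Height Velocity SDS over 52 weeks for weekly TransCon hGH and daily hGH treatment groups". Nothing limits HV SDS to Week 52 or adjusts the reference SD for shorter intervals.

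**The concern.** An SD score is meant to say how many population SDs a child lies from the reference mean. For that, the SD in the denominator must describe velocities measured over the same length of time as the child's own. Height measurement error enters annualised HV multiplied by 365/days, so velocities over short intervals vary more among normal children than velocities over a year. The SAP divides both by the same SD.

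If the reference SD belongs to roughly one year, the Week 5 and Week 13 scores would look far more dispersed than true SD scores. Each would also appear further from normal than it is. The spread in Figure 11 would narrow over the year partly because the annualisation factor falls, not because children become more alike. SAP section 1 allows planned analyses to go into study reports, submissions and manuscripts, where readers will take an SDS at face value.

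**Working it through.** The documents give no figure for HV SDS, so there is none to reproduce.

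**Inputs from the documents.** The target study days in SAP Table 3 are 29, 88, 179, 270 and 365. Subtracting Day 1 gives intervals of 28, 87, 178, 269 and 364 days. The annualisation factor is 365/days (SAP 6.2).

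**Assumed inputs, not in the documents.**

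- SD of one height measurement: e = 0.3 cm, range 0.2-0.5.
- Reference SD: s = 1.0 cm/year, range 0.7-1.5.
- The reference SD applies to a one-year interval.
- A child's true velocity has the same spread over every interval, so only measurement error changes with the interval.

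**Step 1. Error SD of annualised HV.** A velocity uses two heights, so the error SD is sqrt(2) x e x 365/days. At Week 5 with e = 0.3 this is 1.414 x 0.3 x 13.04 = 5.53 cm/year.

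**Step 2. SD of the SDS in a reference child.** A one-year reference SD already contains about 2e² of error variance, which leaves s² - 2e² for true velocity. At interval t the SD of the SDS is sqrt(s² - 2e² + 2e²(365/t)²) / s. A valid score has the value 1. At Week 5: sqrt(1 - 0.18 + 5.53²) = sqrt(31.4) = 5.60.

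| Visit | Days | 365/days | Error SD, cm/year (e = 0.3; range 0.2-0.5) | SD of SDS (e = 0.3, s = 1.0) |
|---|---|---|---|---|
| Week 5 | 28 | 13.04 | 5.53 (3.69-9.22) | 5.60 |
| Week 13 | 87 | 4.20 | 1.78 (1.19-2.97) | 2.00 |
| Week 26 | 178 | 2.05 | 0.87 (0.58-1.45) | 1.26 |
| Week 39 | 269 | 1.36 | 0.58 (0.38-0.96) | 1.07 |
| Week 52 | 364 | 1.003 | 0.43 (0.28-0.71) | 1.00 |

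The ratio of Week 5 to Week 52 is 364/28 = 13.0 and does not depend on e.

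**Step 3. Error in SDS units at Week 5.** The central value is 5.53/1.0, about 5.5. With both assumptions varied, the range runs from 3.69/1.5 = 2.5 to 9.22/0.7 = 13.2. The upper corner is an outer bound: with e = 0.5 the one-year error SD (0.71) already slightly exceeds a reference SD of 0.7.

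**Step 4. Can the age lookup absorb this?** The mean age used is age at Visit 1 plus 14 days at Week 5 and plus 182 days at Week 52. The difference is 168 days, or 0.46 years. A shift of that size in the age lookup cannot offset a 13-fold change in the error term.

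**Step 5. Position of a score.** Suppose a child grows 5 cm/year faster than the reference mean. With s = 1.0 the SAP scores this +5 at both visits. Against the interval-matched SD of 5.6, the Week 5 score would be 5/5.6, about +0.9.

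**The case against.** Several objections have force.

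*The formula alone does not prove the point.* With steady growth and perfect measurement, annualised HV would have the same spread at every interval. This is correct: some height error is needed, and its size is assumed. But any non-trivial height error is multiplied 13-fold, so the incompatibility stands. Only its size is uncertain.

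*The documents do not show which visits are wrong.* A reader might infer from the SAP alone that the early scores are the invalid ones. The documents do not support that by themselves, because the interval of the reference SD is not stated. Two features point to one year: HV is expressed in cm/year, and the baseline HV rule in SAP 6.2 picks the height closest to one year before baseline. It remains an assumption.

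*The early spread is not all noise.* A reader might infer that the spread at Weeks 5 and 13 is mostly measurement error. Taking the planning SD of 3.5 cm/year (SAP 3.2) as a rough measure of true spread, the error share of variance at Week 5 is 5.53²/(5.53² + 3.5²) = 71% (53-87% over the assumed error range). At Week 13 it is only 21% (10-42%). The inference fails at Week 13.

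*A falling mean SDS is not an artefact of error.* Zero-mean error widens the spread but does not move the mean. With an almost constant denominator, a fall in mean SDS would reflect a fall in mean HV. Only the narrowing of the spread is partly artefact.

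*Little depends on it.* HV SDS is not a listed endpoint (SAP 2.2.1), has no planned model or test, and is outside the hierarchy in SAP 8.6. Both arms use the same formula. All of this stands and keeps the point minor.

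**Conclusion.** The concern holds as a minor point about descriptive displays. From the SAP's own rules, together with any non-trivial height error, one reference SD cannot serve both a 28-day and a 364-day velocity. If that SD is for about one year, the Week 5 scores are badly distorted (SD about 5.6 where 1 is expected) and the Week 13 scores clearly so (about 2.0). The effect is modest at Week 26 (1.26), small at Week 39 (1.07) and absent at Week 52. These sizes rest on the assumed height error of 0.3 cm, the assumed reference SD of 1.0 cm/year and the assumed one-year reference interval.

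A reader might also infer that the primary result is at risk. It is not: the primary comparison uses HV in cm/year at Week 52, and HV SDS plays no part in it.

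**What to change.** In SAP 6.2, state the interval to which the reference SD applies. In SAP 6.2 and 8.2, report HV SDS only at visits whose interval matches it, which means Week 52 if it is a one-year SD.

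At the least, remove Weeks 5 and 13 from Tables 14.2.2.4 and 14.2.2.5 and Figure 11. If Weeks 26 and 39 are kept, add a footnote that the reference SD applies to a longer interval. Earlier visits could be kept in full only with reference SDs matched to each interval.

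The cost is a sentence or two in the SAP and fewer table cells. The downside is that HV SDS is not shown at early visits. The time course remains visible in Height SDS by visit (Table 14.2.2.1, Figures 9 and 10) and in HV in cm/year by visit (Table 14.2.1.1).
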